7.1.3 Subject Daily Diary

The subject daily diary will be completed by the subject every evening starting at screening for Pathway 3 - *de novo* subjects and starting the day of randomization Visit 1/Day 0 for Pathways 1 and 2. Subject diary will consist of questions regarding IMP daily intake, stool frequency, and presence of blood content.

The score for stool frequency and rectal bleeding will be calculated as an average based on scores collected from subject diary data 5 days prior to Visits 1, 2, 3, 4, and 5 (see [Appendix 2](#)). If a subject recorded fewer than 3 days of scores during this 5-day period, the average score will be considered missing.

The subject daily diary and questionnaire will be completed via a validated Interactive Voice Response System (IVRS). Instructions on the use of the subject daily diary and questionnaire will be provided to each trial center.

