3.2 Determination of Sample Size

The true remission rates at Month 6 for mesalamine 2 g extended release granules (sachet) and placebo regimens were assumed as 68% and 49%, respectively, based on The mesalamine Study Group (1996)(3), Hawkey et al (1997)(4), and Apriso™ package insert (2009)(5). Under these assumptions, a sample size of 120 randomized subjects per group will provide at least 85% power to detect a statistically significant treatment group difference in the remission rate at a two-sided 0.05 significance level using the chi-square test. To maintain the power for the primary efficacy analysis that excludes subjects who are rolled over from the placebo group in the 000174 trial via Pathway 1, approximately 260 subjects will be randomized.

4 Subject Disposition

The number of screened subjects will be summarized, and for subjects not randomized, the primary reason for exclusion from randomization will be summarized.

The number and percentage of subjects who are randomized, are treated with IMP, prematurely discontinued, and completed the trial will be summarized with the reason of premature discontinuations.

The time to discontinuation will be summarized by the Kaplan-Meier estimates, and the treatment group difference will be tested by the log-rank test. In addition, reason-specific discontinuation will be summarized by the cumulative incidence estimates.

5 Protocol Deviations

The following protocol deviations will be identified as major protocol deviations:

- Overall IMP compliance of less than 80%
- Not taking the randomized IMP
- Taking prohibited medications

The final definition of major protocol deviations will be determined prior to breaking the blind.

The number and percentage of subjects with protocol deviations will be summarized.

6 Analysis sets

For each analysis set, the number and percentage of subjects excluded from it will be summarized by the reason of the exclusion.

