9.1 General Considerations

All statistical tests will be conducted at a two-sided 0.05 significance level.

All secondary endpoints will be tested without adjustment for multiplicity.

Randomization strata will be included in stratified analyses for efficacy endpoints. For the ITT, mITT, and PP analysis sets, randomization strata will be defined as follows:

- Stratum 1: Pathway 1 (mesalamine 4 g extended release granules arm in the 000174 trial)
- Stratum 2: Pathway 2
- Stratum 3: Pathway 3

Randomization strata for the all randomized analysis set will be defined as follows:

- Stratum 1: Pathway 1a (placebo arm in the 000174 trial)
- Stratum 2: Pathway 1b (mesalamine 4 g extended release granules arm in the 000174 trial)
- Stratum 3: Pathway 2
- Stratum 4: Pathway 3

Stool frequency and rectal bleeding scores at each visit will be calculated as an average of the daily scores collected within 5 days prior to the visit (excluding the visit day and the day before the visit day if the bowel preparation is needed on the day before the visit). If the daily scores in this period are available for fewer than 3 days, the average score will be considered missing. The average scores will be rounded to the nearest integer for the final score determination (e.g., 0.3 will be rounded to 0, and 0.5 will be rounded to 1). Handling of missing data in the statistical analyses will be described for each endpoint.

For the endoscopic assessment, the outcomes determined by the independent central reading procedure will be used for all analyses.

For visit-based data, the data collected on the day that is closest to the scheduled trial day within a window will be assigned to the corresponding analysis visit. [Table 2](#) shows the scheduled trial day and window for each analysis visit.

Table 2 Scheduled trial day and window for analysis visits

Analysis visit	Scheduled trial day	Window
Baseline	Day 1	prior to the first dose of IMP

Analysis visit	Scheduled trial day	Window
Week 2	Day 14	Day 1 to Day 35
Month 2	Day 56	Day 36 to Day 84
Month 4	Day 112	Day 85 to Day 140
Month 6	Day 168	Day 141 or after

If the closest day cannot be uniquely identified for an analysis visit, the data collected on an earlier trial day will be assigned to the analysis visit.

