9.2 Primary Endpoint(s)

9.2.1 Primary Variable(s) Analysis

The primary efficacy analysis will be based on the ITT analysis set. The proportion of subjects in remission, defined as rectal bleeding of 0 and stool frequency scores of 0 or 1 with an endoscopic score of 0 or 1 in the Clinical and Endoscopic Response Score at Month 6, will be assessed by the Mantel-Haenszel test stratified by the randomization strata at a two-sided 0.05 significance level. Subjects who discontinue the double-blind regimen before Month 6, as well as subjects with missing remission assessment at Month 6, will be considered not having met the remission criteria. The common odds ratio will be estimated using the Mantel-Haenszel adjusted odds ratio estimate, and its 95% confidence interval will be provided. The homogeneity of odds ratios across the randomization strata will be tested by the Breslow-Day test at a 0.05 significance level, and the odds ratio for each stratum will be presented in forest plots. The quantitative or qualitative nature of the possible treatment by stratum interaction will be assessed and discussed.

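### Where the bowel-preparation day is dropped from the Month 6 diary window, the unchanged 3-day minimum makes some remitters missing and so primary failures

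*SAP*

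**What the plan says.** Protocol 7.1.3 scores stool frequency and rectal bleeding as averages over the 5 diary days before each visit. Its evaluability rule is: "If a subject recorded fewer than 3 days of scores during this 5-day period, the average score will be considered missing". It has no exclusion for bowel preparation.

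SAP 9.1 uses the same 5-day period but adds a conditional exclusion: "excluding the visit day and the day before the visit day if the bowel preparation is needed on the day before the visit". It then states: "If the daily scores in this period are available for fewer than 3 days, the average score will be considered missing". Nothing adds a day back, and the minimum is not changed.

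In the primary analysis (SAP 9.2.1), subjects who stop early, "as well as subjects with missing remission assessment at Month 6, will be considered not having met the remission criteria". SAP 9.3 likewise imputes missing clinical remission as non-remission in the GEE analysis.

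In the schedule of procedures, endoscopy after baseline is planned only at Visit 5 (Month 6 or early withdrawal). SAP section 12 declares no deviation from the protocol's planned analysis.

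**The concern.** The exclusion itself is sensible, because preparation distorts that day's stool count. The trouble is its side effect. Once Day -1 is removed from a fixed 5-day span, Days -5 to -2 remain and the subject still needs three entries. That subject may miss one diary day at Month 6, against two at Months 2 and 4, where no endoscopy is scheduled.

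Month 6 supplies the primary endpoint, and a missing score there counts as loss of remission. Some subjects with a quiet endoscopy and no recorded symptoms would therefore fail because of diary gaps, even though the diary is kept every evening and an earlier entry, such as Day -6, may exist unused. The same subjects become non-remitters in the Month 6 GEE estimate. At stake are an attenuated treatment difference, some power, and a primary-endpoint rule that differs from the protocol without being declared.

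**Working it through.** **Inputs from the documents.** Assumed remission for mesalamine and "placebo regimens were assumed as 68% and 49%, respectively" (SAP 3.2); "a sample size of 120 randomized subjects per group will provide at least 85% power" (SAP 3.2); two-sided 0.05 (SAP 9.1); 3 of 5 days (protocol 7.1.3); 3 of 4 days after deletion of Day -1 (natural reading of SAP 9.1).

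**Assumptions, not in the documents.** Daily diary completion q of 95%, 90% or 80%, independent between days, equal in both arms and unrelated to remission. Share of subjects needing preparation the day before Month 6: all, or half. Diary gaps are the only source of loss.

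**Step 1: the plan's power.** With mean rate 0.585,

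power = Φ{[0.19√120 − 1.960√(2 × 0.585 × 0.415)] / √(0.68 × 0.32 + 0.49 × 0.51)} = Φ[(2.081 − 1.366)/0.684] = Φ(1.047) = 85.2%.

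This agrees with the stated figure.

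**Step 2: who is affected.** A subject changes from evaluable to missing only with an entry on Day -1 and on exactly two of the other four days. The probability is q × 6q²(1−q)² = 6q³(1−q)². At q = 0.90 it is 6 × 0.729 × 0.01 = 4.4%.

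**Step 3: total missingness.**
- 3 of 5: 1 − [10q³(1−q)² + 5q⁴(1−q) + q⁵]. At q = 0.90: 1 − (0.0729 + 0.3281 + 0.5905) = 0.9%.
- 3 of 4: 1 − [4q³(1−q) + q⁴]. At q = 0.90: 1 − (0.2916 + 0.6561) = 5.2%.

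**Step 4: power.** Multiply both remission rates by (1 − missing) and repeat Step 1 with 120 per group. At q = 0.90 the rates are 67.4% vs 48.6% under 3 of 5 and 64.4% vs 46.4% under 3 of 4. If half need preparation, missingness is the mean of the two rules: (0.9% + 5.2%)/2 ≈ 3.0%, giving 65.9% vs 47.5%.

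| Daily completion | Missing, 3 of 5 | Missing, 3 of 4 | Extra | Power, 3 of 5 | Power, 3 of 4, all prepared | Power, half prepared |
|---|---|---|---|---|---|---|
| 95% | 0.1% | 1.4% | 1.3% | 85.1% | 84.0% | 84.6% |
| 90% | 0.9% | 5.2% | 4.4% | 84.5% | 80.5% | 82.5% |
| 80% | 5.8% | 18.1% | 12.3% | 80.0% | 67.7% | 74.0% |

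**Step 5: in subjects.** Remitters turned into failures per 120 are 120 × rate × extra. With all prepared this gives 1.0 mesalamine and 0.8 placebo at 95% completion, 3.6 and 2.6 at 90%, and 10.0 and 7.2 at 80%.

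**Step 6: slack.** The 120 per group just reaches 85%. The increase to "approximately 260 subjects will be randomized" is explained only by the Pathway 1 placebo roll-overs left out of the primary analysis, so it was not planned to absorb diary loss.

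**The case against.** **The text may mean five eligible days.** The visit day already lies outside a window before the visit, so excluding it deletes nothing. The parenthesis could therefore be defining which days count, with five eligible days kept and no loss. This reading is possible, but the SAP has no words that move the window back, and it applies the minimum to the stated period. Two programmers could derive different primary outcomes, and the same sentence would settle it.

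**The exclusion is conditional.** This stands. Month 6 may be a flexible sigmoidoscopy or a colonoscopy, and the documents do not say how often preparation falls on the day before. A reader might infer that every subject faces 3 of 4 at Month 6; the text does not support that.

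**Low diary completion is unlikely.** This partly stands. Subjects unable to complete the diary are excluded (protocol 4.1.2), and diary compliance is assessed at visits from Visit 2 (protocol 7.2.9). IMP compliance is computed from the diary (SAP 8.2), with below 80% a major deviation (SAP section 5). The 80% row is an extreme case; at 95% completion the cost is about one point of power.

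**Multiple imputation covers it.** SAP 9.2.2 imputes missing Month 6 clinical scores under a missing-at-random and a control-based model. These test robustness to this missingness, but they are sensitivity analyses and leave the primary test as it is.

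**Three uncontaminated days is a fair quality floor.** It is, and the proposed change keeps it.

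**Conclusion.** The point holds as a flaw in the evaluability rule for subjects who need preparation the day before Month 6. On the natural reading, SAP 9.1 tightens 3 of 5 to 3 of 4, and the preparation-day exclusion is absent from protocol 7.1.3 although SAP section 12 declares no deviation. If every subject needs such preparation, the cost relative to 3 of 5 is about 1 point of power at 95% completion, 4 at 90% and 12 at 80%. If half do, it is about 0.6, 2 and 6 points. All of this rests on independent daily completion at assumed rates.

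Three stronger conclusions might be inferred and are not supported:
- **Every diary gap harms the subject.** Someone who missed two of Days -5 to -2 and also Day -1 is missing under the protocol too. For the same reason, the whole fall from 85.2% cannot be charged to the SAP; the fair comparison is with the 3-of-5 column.
- **The rule favours mesalamine.** The loss is expected to be similar in both arms. It shrinks the difference (at 90% completion with all prepared, from 18.8 to 18.0 points).
- **A fall in clinical remission from Month 4 to Month 6 is an artefact.** Part of one could be, but in both arms, and the SAP plans no within-arm test of that change.

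**What to change.** Before unblinding, state in SAP 9.1 that when the preparation day is excluded, the score uses the 5 most recent eligible diary days (Days -6 to -2), with the minimum of 3 kept. Apply this to the primary endpoint and to clinical remission at Month 6. List both the preparation-day exclusion and this window in SAP section 12. It would also help to report, by arm, how many subjects had a day excluded and how many would change evaluability.

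The cost is one sentence in 9.1 and one entry in section 12. No new data are needed, since the diary is completed daily. The downside is that one diary day is a day older and falls outside the protocol's 5-day window, which is why the entry in section 12 is needed.

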4.4 Withdrawal Criteria

Subjects have the right to withdraw from the trial at any time for any reason, without the need to justify their decision. However, the investigator should record the reason for the subject's withdrawal. The investigator also has the right to withdraw subjects.

Subjects will be withdrawn in the following cases:

- pregnancy at any time during the trial will be a reason for withdrawal
- withdrawal of consent
- worsening of UC with a need for an escalation of the therapy (i.e., surgical therapy, use of steroids, immunosuppressive or immunomodulating drugs, biologics, increase dose of 5-ASA in any form)
- request for termination of the trial by regulatory authorities or sponsor
- the subject develops any AE that, in the opinion of the investigator, warrants the subject's withdrawal from treatment. An AE form will be completed as appropriate, and the subject will be followed until the event is clinically stable.

For subjects who discontinue due to an AE, all efforts will be made to follow the outcome of the AE and to assess the efficacy criteria.

For any discontinuation, the investigator will obtain all the required details and document the date of the premature termination and the main reason in the electronic case report form (eCRF). Since an excessive rate of withdrawals can render the trial devoid of meaning, the unnecessary withdrawal of subjects should be avoided.

Subjects who withdrew from the trial will not be replaced.

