6 TRIAL PROCEDURES

6.1 Trial Flow Chart

The schedule of trial procedures is presented in [Table 1](#).

Table 1: Schedule of Trial Procedures

	Screening ^a	Baseline/ Randomization ^b	Intermediate	Intermediate	Intermediate	End of Treatment/ Early Withdrawal
Visit	0	1	2	3	4	5
Month ^c	Week - 3	Month 0	Week 2	Month 2	Month 4	Month 6
Trial Day (visit window)	Up to Day -21	Day 0	Day 14 (±3 days)	Day 56 (±5 days)	Day 112 (±5 days)	Day 168 (±5 days)
Written informed consent	X	X ^d				
Inclusion/exclusion criteria review	X	X				
Medical history	X	X				
Physical examination, including weight	X	X	X	X	X	X
Height	X					
Vital signs	X	X	X	X	X	X
12-lead electrocardiogram	X					X
Demographic data	X					
Serum/urine pregnancy test ^e	X	X				X
Standard urinalysis ^f	X ^g					X
Drug and alcohol history	X					
Immunological testing for HBV, HCV, and HIV	X					
Estimated creatinine clearance	X ^g		X	X	X	X
Safety hematology, coagulation, and chemistry	X ^g		X ^m	X	X	X
Randomization		X				
Prior and concomitant medications	X	X	X	X	X	X
Serum CRP		X ^a		X	X	X
Fecal calprotectin stool sample		X ^a		X	X	X
Clinical Response Score (stool frequency and rectal bleeding scores)	X			X	X	
Calculation of Clinical and Endoscopic Response Score		X ^h				X
Flexible sigmoidoscopy /colonoscopy ⁱ - Central reading	X					X
HRQoL questionnaire: IBDQ		X ^a		X	X	X
Adverse event recording ^j	X	X	X	X	X	X
Distribution of trial medication		X		X	X	
First administration of trial medication		X ^l				
Trial medication collection/accountability			X ⁿ	X	X	X
Trial medication compliance			X	X	X	X
Subject diary activation	X	X ^d				
Subject diary data review ^k		X	X	X	X	X

Note: All subjects who discontinue treatment will complete end-of-treatment assessments.

- a For Pathway 3 - *de novo* subjects only (a complete screening visit, including flexible sigmoidoscopy/colonoscopy which will be scheduled at screening and completed at least (4) days prior to randomization).
- b Subjects in Pathways 1 and 2 will be consented at Visit 1/Baseline. The complete screening assessments will be taken from Study 000174 end-of-treatment visit and eligibility (all inclusion/exclusion criteria) will be reassessed.
- c Month equals 4 weeks; week equals 7 days.
- d Pathways 1 and 2 only.

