6.2.5 End-of-Treatment / Early Withdrawal Visit: Visit 5 (Day 168 ±5)

The following will be performed/collected at Visit 5:

- physical examination, including weight
- vital signs (blood pressure and pulse rate)
- 12-lead ECG
- urine pregnancy testing (test strip) for females of childbearing age or <1 year postmenopausal
- estimated creatinine clearance
- clinical safety laboratory assessment: chemistry, hematology, coagulation, standard urinalysis
- concomitant medication review
- serum CRP and fecal calprotectin levels
- Clinical and Endoscopic Response Score (Table 2), based on the subject recording of stool frequency and rectal bleeding in the daily diary, and flexible sigmoidoscopy/colonoscopy

- flexible sigmoidoscopy/colonoscopy
- submit flexible sigmoidoscopy/colonoscopy recording to central reader
- IBDQ
- assessment of any AEs since the previous visit
- collection of trial medication
- review of subject daily diary data including compliance, and deactivation of subject daily diary
- trial medication compliance assessment

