9.6.3 Secondary Endpoints

Secondary endpoints are the following:

1. The proportion of subjects in clinical remission at Months 2, 4, and 6, defined as a score of 0 for rectal bleeding and 0 or 1 for stool frequency based on Clinical Response Score subset of the Clinical and Endoscopic Response Score
2. Time to relapse, defined as number of days from randomization to the day of withdrawal due to escalation of therapy (i.e., surgical therapy, use of steroids, immunosuppressive or immunomodulating drugs, biologics, increase dose of 5-ASA in any form)
3. The proportion of subjects with an increase from baseline in the Clinical and Endoscopic Response Score by 2 or more points in at least 1 component or by 1 or more points in at least 2 components at Month 6

4. The change from baseline in serum CRP levels at Months 2, 4, and 6
5. The change from baseline in fecal calprotectin levels at Months 2, 4, and 6
6. The change from baseline to each scheduled assessment for published and validated domain scores of the IBDQ
7. Safety assessed by incidence and severity of AEs and abnormal laboratory values

The proportion of subjects in clinical remission at Months 2, 4, and 6 will be analyzed by the generalized estimating equations approach as longitudinal binary outcomes. The model will include randomization strata, treatment, time, and treatment- by-time interaction. The clinical remission rates and odds ratios will be estimated for each time point.

The time to relapse will be analyzed by a log-rank test stratified by the randomization strata.

The change from baseline in serum CRP and fecal calprotectin levels will be assessed with a repeated-measures analysis of covariance (ANCOVA) model that includes randomization strata, treatment, time, and treatment-by-time interaction as fixed effects, and baseline value as a covariate based on the observed data. The adjusted changes from baseline and their difference between treatment groups will be estimated for each time point.

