The change from baseline in serum CRP levels and fecal calprotectin levels at Months 2, 4, and 6 will be analyzed by repeated-measures analysis of covariance (ANCOVA) models that include the randomization strata, treatment, time, and treatment-by-time interaction as fixed effects, and the corresponding baseline value as a covariate. The adjusted changes from baseline and their difference between treatment groups will be estimated for each time point. The overall treatment difference over 6 months will be estimated as the main effect for treatment in the model. The missing values will be left as missing, and an unstructured correlation matrix will be assumed.

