9.4 Other Endpoint(s)

9.4.1 Health Related Quality of Life

The change from baseline in the IBDQ will be analyzed for the ITT analysis set.

The following domain scores for the IBDQ (Guyatt et al., 1989)(9) will be calculated by adding up scores from questions included in the domain for each subject at each time point:

- Bowel symptoms: Questions 1, 5, 9, 13, 17, 20, 22, 24, 26, 29
- Emotion function: Questions 3, 7, 11, 15, 19, 21, 23, 25, 27, 30, 31, 32

- Systemic symptoms: Questions 2, 6, 10, 14, 18
- Social function: Questions 4, 8, 12, 16, 28

The total score will be calculated by adding up all scores for each subject at each time point.

The handling of missing score in the calculation of the domain and total scores will be based on McMaster University (2010)(10). If there is only one missing response within a domain, the missing response will be imputed as an average of other responses within the domain. If there are two or more missing responses within a domain, the domain score will be considered missing.

If there are up to four missing responses, the missing responses will be imputed as an average of other responses. If there are more than four missing responses, the total score will be considered missing.

The change from baseline in the IBDQ domain and total scores at Months 2, 4, and 6 will be analyzed by repeated-measures ANCOVA models that include treatment, randomization strata, time, and treatment-by-time interaction as fixed effects, and the corresponding baseline value as a covariate. The adjusted changes from baseline and their difference between treatment groups will be estimated for each time point. The missing values will be left as missing, and an unstructured correlation matrix will be assumed.

10 Safety

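### Should CRP, calprotectin and IBDQ values taken at early withdrawal be given a rule of their own, or a sensitivity analysis, when the visit windows leave them out of the models?

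*SAP*

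**What the plan says.** **Collection.** The note to Protocol Table 1 (section 6.1) reads "All subjects who discontinue treatment will complete end-of-treatment assessments". Visit 5, which doubles as the early-withdrawal visit (Protocol 6.2.5), includes "serum CRP and fecal calprotectin levels" and the IBDQ. For withdrawals due to an adverse event, Protocol 4.4 adds that "all efforts will be made to follow the outcome of the AE and to assess the efficacy criteria".

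**Assignment.** SAP 9.1 assigns visit data by trial day: "the data collected on the day that is closest to the scheduled trial day within a window will be assigned to the corresponding analysis visit". The Table 2 windows are Week 2, Days 1-35; Month 2, Days 36-84; Month 4, Days 85-140; Month 6, Day 141 onward. On a tie, "the data collected on an earlier trial day will be assigned to the analysis visit". Nothing distinguishes a withdrawal visit from a scheduled one.

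**Analysis.** Protocol 9.6.3 specifies a repeated-measures model for CRP and calprotectin with "baseline value as a covariate based on the observed data", and Protocol 9.6.4 does the same for IBDQ. SAP 9.3 models CRP and calprotectin at Months 2, 4 and 6 and states: "The missing values will be left as missing, and an unstructured correlation matrix will be assumed". SAP 9.4.1 matches it: "The change from baseline in the IBDQ domain and total scores at Months 2, 4, and 6 will be analyzed by repeated-measures ANCOVA" models. Week 2 is in none of them.

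**Sensitivity analyses.** The last-observed, multiple-imputation and pattern-mixture analyses in SAP 9.2.2 concern the primary remission endpoint. The end-of-treatment rule in SAP 10.3 concerns safety laboratory variables, and the list in Protocol 7.1.7 includes neither CRP nor calprotectin.

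**The concern.** Worsening colitis that needs escalated therapy is a withdrawal reason (Protocol 4.4), and no follow-up comes after participation ends (Protocol 3.5.8). The withdrawal sample is therefore the last one such a subject gives, and it may be the one that records the flare. A repeated-measures model that leaves missing values missing relies on dropout being explained by the data in the model. If a collected value that bears on that assumption is set aside, and flare withdrawals differ between arms, the estimated differences in CRP, calprotectin and IBDQ could be biased. The sponsor planned checks against informative dropout for the primary endpoint but states none for these three measures. It is natural to ask why values already collected should go unused.

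**Working it through.** The plan gives no figure on this point. Its one power statement concerns the primary endpoint and is untouched. With 68% vs 49%, 120 per group and two-sided 0.05, the pooled-variance formula gives z = (0.19 × √120 − 1.96 × √(2 × 0.585 × 0.415)) / √(0.68 × 0.32 + 0.49 × 0.51) = (2.081 − 1.366) / 0.684 = 1.05. Power is 85.2%, which agrees with the stated 85% or more.

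**1. Which withdrawal days go unused.** Apply Table 2 to a withdrawal on each of Days 1-167, with Month 2 attended on Day 56 and Month 4 on Day 112.

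| Withdrawal day | Fate of the value | Days |
|---|---|---|
| 1-35 | Week 2, not modelled | 35 |
| 36-56 | used as Month 2 | 21 |
| 57-84 | unused; Day 56 value kept | 28 |
| 85-112 | used as Month 4 | 28 |
| 113-140 | unused; Day 112 value kept | 28 |
| 141-167 | used as Month 6 | 27 |

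Unused: 35 + 28 + 28 = 91, and 91/167 = 54.5%. No post-baseline value in the model: 35/167 = 21.0%. Scheduled value kept: 28 + 28 = 56.

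**2. Effect of visit timing.** Under the protocol's ±5-day windows, a visit on Day 61 leaves Days 62-84 unused (23 days). A visit on Day 51 leaves Days 61-84 unused (24 days), because withdrawal values from Days 52-60 are closer to Day 56 and replace the attended one. Month 4 behaves the same way. The total runs from 35 + 23 + 23 = 81 to 91. With one of the two visits missed it is 58 to 63; with both missed, 35. The 35 days without a post-baseline value are the same in every case.

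**3. From days to subjects (assumptions).** The documents give no dropout rate or timing. Suppose 15-50% withdraw by Month 6. The share of withdrawals on Days 1-35 is then 22-27% under a constant hazard, 33-39% if front-loaded (Weibull shape 0.75) and 5-6% if late-loaded (shape 2). As a separate illustration, let 25-100% of the assumed non-remitters withdraw, evenly over Days 1-167. Non-remitters number 120 × 0.32 + 120 × 0.51 = 99.6. Then 99.6 × 35/167 = 20.9 at 100% and 5.2 at 25%, so about 5 to 21 subjects in total would have no post-baseline value.

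**4. Would using the values help?** The obvious check refits the models with the values moved to the next modelled visit. A value from Day 1 labelled Month 2 moves 56 − 1 = 55 days; Day 57 to Month 4 and Day 113 to Month 6 move the same distance. Whether this approaches a Month 6 difference depends on how much of the flare rise would still be present.

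An illustrative simulation used 300 trials of 120 per arm, three equal strata, between-subject SD 0.7, residual SD 0.6, a flare rise of 1.8 units, flare withdrawal of 30% on placebo and 15% on active, and 10% non-flare withdrawal per arm. All these inputs except the arm size are assumed. It moved every withdrawal value found in the Week 2 window or in a window already filled. The Month 6 difference was −0.07 under Table 2 and −0.16 with values moved. The target is −(0.30 − 0.15) × 1.8 × persistence = −0.27 × persistence. Errors below come from unrounded estimates.

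| Persistence | Target | Error, Table 2 | Error, moved |
|---|---|---|---|
| 0% | 0 | 0.07 | 0.16 |
| 25% | −0.07 | 0.01 | 0.10 |
| 50% | −0.14 | 0.06 | 0.03 |
| 75% | −0.20 | 0.13 | 0.04 |
| 100% | −0.27 | 0.20 | 0.11 |

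Break-even is near ((0.07 + 0.16)/2)/0.27 = 0.115/0.27 = 43%. Over seven non-null scenarios it lay at about 36-54%, with simulation error on top. With equal flare rates, or no rise, the two analyses differed by 0.001.

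**The case for a change.** The case for an added analysis is reasonable. Dropout is tied to outcome by design, the data exist, and the cost is one SAP sentence and seven refits (CRP, calprotectin, four IBDQ domains, IBDQ total). Listings by subject and visit (Protocol 9.6.1) show the values but do not test a treatment difference. It stands that no stated analysis uses these withdrawal values and that these three measures have no stated check against informative dropout.

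It does not follow that the plan is deficient. Neither document promises such a check for these measures. Table 2 covers every post-dose day, so no withdrawal value is left without a defined treatment. The condition for bias, a difference in flare withdrawal between arms, is already visible: time to relapse has a stratified log-rank test and hazard ratio (SAP 9.3), and time to discontinuation is compared by arm with reason-specific cumulative incidence (SAP 4). The refit itself is a form of carrying forward. It also moves non-flare withdrawals, and with persistence unknown a difference between the two results would not show which is closer to the truth. A broad wording that moves any withdrawal value from a filled window would also relabel values Table 2 already uses. With visits on Days 51 and 107 those are Days 52-60 and 108-116, which is 9 + 9 = 18 days' worth.

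Protocol 7.1.4 has CRP measured at every post-baseline visit, whereas Protocol Table 1 shows none at Week 2. This does not alter the point, because the CRP model excludes Week 2 either way.

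**Conclusion.** No change to the plan. The observation is correct: with visits on schedule, 91 of 167 possible withdrawal days (81-91 across the visit windows) give a value that enters no model. The part with real content is smaller. Only Days 1-35, 21.0% of the days, leave a subject with no post-baseline value; otherwise a scheduled value from the same window remains. The number of subjects is unknown without a dropout rate.

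Closest-day assignment with observed data is a pre-specified trade-off. It keeps each value near the time it represents, at the price of leaving some unused. The alternative makes the opposite trade and is not shown to be better; in the illustration it does worse when less than roughly 36-54% of a flare rise persists. That range and the simulated differences rest on assumed inputs and say nothing about the actual size of any bias. What is affected is secondary: CRP, calprotectin and IBDQ, tested without multiplicity adjustment (SAP 9.1). The primary analysis counts discontinuation as non-remission, and time to relapse does not use these values. A statistician who wants to know how many withdrawal values went unused in each arm can count them from the listed data without an SAP amendment.
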